APPENDIX A

Alexandria University
Medical Research Institute
Biomedical Informatics &
Medical Statistics Department

Name: [name]

Sample Size Calculation

The main aim of this study is to demonstrate accuracy of elastosonographic measurements in differentiating benign vs malignant subpleural parenchymal lesions compared to clinical, radiological (CT/PET). A recent study concluded that the ROC curve elaborated for the diagnosis of malignancy by strain elastography showed an AUC of 0.688. ⁽¹⁾ Consequently, patients will be recruited in a cross-sectional sample till achieving the minimum required sample of 60 patients with benign vs 60 patients with malignant subpleural parenchymal lesions with 80% power.

Sample size was calculated using a two-sided, ROC curve test at .05 significance level using R software.

Program Citation:

R Core Team (2017). R: A language and environment for statistical computing. R Foundation for Statistical Computing, Vienna, Austria. URL <https://www.R-project.org/>.

Reference:

Calculated and reported by: [name] [name]
Assistant Professor of Medical Statistics, systematic reviews and Evidence Synthesis. Medical Statistics Department, Medical Research Institute-Alexandria University
Email: [contact]. LinkedIn: [name].
[contact]

[name] [name]
IMAS
26/3/2022

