Direct vibration stimulation on the lung surface is not achievable during lung testing. A vibration stimulation on the chest wall causes surface wave propagation on the lung.⁽¹¹⁾

An ultrasonic probe is used to detect the propagation of the tissue wave motion (usually a few micrometers). By indenting a medium and examining the

relationship between the indentation displacement and the generated force, the indentation technique may determine the elasticity of that medium.⁽¹²⁾

A local mechanical vibration on the chest safely generates the surface wave on the lung in LUSWE. Diagnostic ultrasonography is only utilized to identify the propagation of surface waves on the lung. Strain pictures are created by repeatedly applying modest pressure to the tissues using the transducers.^(13, 14)

Following tissue movement is tracked between pairs of echo frames, and strain is determined based on the axial gradient of the displacements. A stiff area endures less strain (deformation) than surrounding softer tissue when subjected to the same amount of force.^(9, 15)

Most hospitalized patients are not able to perform radiological imaging either due to unavailability or inability to ambulate the patients for imaging to be held. We suggested to perform bedside, relatively cheap and available, imaging modality to help in the differentiation between benign and malignant peripheral lung pathologies.

Lung elastography, to be used as diagnostic tool, is considered a new era worldwide; a new modality that will help to reduce the burden and the widespread use of chest computed tomography.⁽¹⁶⁾

AIM OF THE WORK

The aim of this study is to demonstrate the applicability and efficacy of strain elasto-sonographic measurements in differentiating between benign and malignant peripheral parenchymal lesions.

PATIENTS

This study will include patients recruited in cross-sectional sample till achieving requirement of 120 patients with benign and malignant subpleural parenchymal lesions.

Sample size was calculated by medical research institute and biomedical informatics, Medical Statistics Department, Alexandria University.

(APPENDIX A)

Patients enrolled in our study will be examined and investigated in chest department, in Alexandria Main University Hospitals.

Inclusion criteria:

- 1) Adult patients above age of 18 years old.
- 2) Patients with peripheral lung lesion.

Exclusion criteria:

- 1) Pure pleural lesions.
- 2) Clinical instability to reach the final diagnosis.

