- 3) Inaccessibility by ultrasound.

METHODS

This is a diagnostic accuracy study with comparison to gold standard tests e.g., chest computed tomography, transthoracic biopsy, or microbiological analysis. All patients included in this study will give informed consent according to the guidelines of ethics committee, Alexandria Faculty of Medicine. (<http://www.med.alexu.edu.eg/wp-content/uploads/2012/04/Checklist-FINAL-20141.pdf>)

Informed consent is available at (<http://med.alexu.edu.eg/alexuniv/wp-content/uploads/2021/09/Standard-Operating-Procedure-2020-ethics.pdf>).

All patients will be subjected to:

- 1) Thorough history taking.
- 2) Complete physical examination.
- 3) CT scan chest.
- 4) Routine laboratory investigation profile.
- 5) Conventional methods to reach final diagnosis such as microbiological analysis, CT scan, fiberoptic bronchoscopy, and image guided biopsies.
- 6) Strain elastography done by superficial and deep probes, in which B mode is compared with the elastography image for real time assessment; strain ratio is obtained. Strain ratio between benign and malignant peripheral lung lesions to be evaluated.

Data collected from our research aim to estimate a cut-off value by which benign and malignant peripheral parenchymal lesions to be easily discriminated by ultrasonographic elastography.

Statistical methods:

Considering nominal data e.g., clinical features, CT findings, epidemiology, smoking status, and final diagnosis will be statistically analyzed using median, mode, MANN-WHITNEY, and Chi square tests.

While numerical data analysis as arithmetic mean is helpful in situation of age statistical distribution. Strain ratio interpretation, the telltale sign of our study, is directed towards comparison of the cut off value achieved with the final diagnosis of the patients.

Receiver operator characteristic (ROC) curve will be plotted to evaluate and assess the sensitivity and specificity of strain ratio obtained from elastography compared to final diagnosis for 60 of our patients from the total 120 patients recruited in the study.

While according to the remaining 60 patients, a multivariate Cox proportional hazard analysis would be held to validate and evaluate results obtained from the former 60 examined patients.

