At the end of the study, sensitivity, specificity, area under the curve (AUC), accuracy of a certain cut-off value, positive predicted value (PPV) and negative predicted value (NPV) would describe the performance of strain ratio as a diagnostic tool in the main aim of the research.

ETHICS OF RESEARCH

Research on human or human products:

- Prospective study: Informed consent will be taken from patients. In case of incompetent patients, the informed consent will be taken from the guardians.
- Retrospective study: Confidentiality of records will be considered
- DNA / genomic material: Informed consent for DNA / genomic test and research will be taken from patients. No further tests will be carried out except with further approval of committee and patients. If the samples will travel outside Egypt, the researcher will be responsible for transportation and security approval.
- All drugs used in the research are approved by the Egyptian Ministry of Health

Research on animal:

- The animal species are appropriate for the test.
- After test, if the animal will suffer, it will be euthanized and properly disposed.
- After operation, it will have a proper postoperative care.

سأقوم بتسلیم الموافقات المبنیة على علم المريض الخاصة بالدراسة عند الانتهاء منها او عند طلبها
من اللجنة

RESULTS

The results obtained from this study will be tabulated and statistically analyzed using appropriate statistical methods and appropriate figures and diagrams.

DISCUSSION

The results obtained from this study will be discussed in the view of achievement of the aim and will be compared with any of the available published data in the same field of the research.

REFERENCES

1. Beach KW. 1975-2000: a quarter century of ultrasound technology. *Ultrasound Med Biol*. 1992;18(4):377-88.
2. Volpicelli G. Lung sonography. *J Ultrasound Med*. 2013;32(1):165-71.

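### The stated 80% power belongs to a ROC test on 60 benign plus 60 malignant patients, but the only ROC analysis specified uses 60 of the 120, and no null AUC is given

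*Combined protocol and SAP*

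**What the plan says.** Appendix A sets "the minimum required sample of 60 patients with benign vs 60 patients with malignant subpleural parenchymal lesions with 80% power". It describes the calculation in one sentence: "Sample size was calculated using a two-sided, ROC curve test at .05 significance level using R software". An AUC of 0.688 is cited from an earlier study. Appendix A gives no null AUC, and it names neither a formula nor an R function.

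The Patients section repeats only the total: "patients recruited in cross-sectional sample till achieving requirement of 120 patients with benign and malignant subpleural parenchymal lesions".

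The Methods section aims at a cut-off: "Data collected from our research aim to estimate a cut-off value by which benign and malignant peripheral parenchymal lesions" are to be told apart. The Statistical methods section then says: "Receiver operator characteristic (ROC) curve will be plotted to evaluate and assess the sensitivity and specificity of strain ratio obtained from elastography". The same sentence limits this curve to half of the sample: "compared to final diagnosis for 60 of our patients from the total 120 patients recruited in the study". The benign/malignant make-up of those 60 is not given. The other half goes elsewhere: "While according to the remaining 60 patients, a multivariate Cox proportional hazard analysis would be held to validate" the results from the first 60.

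That section closes with a list of measures for the main aim: "At the end of the study, sensitivity, specificity, area under the curve (AUC), accuracy of a certain cut-off value", followed by the predictive values. It does not say whether they come from the first 60, the second 60 or all 120.

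**The concern.** The sample size rests on one test, a ROC test on 120 patients in two equal groups. The analysis text contains no such test. Its only ROC curve uses half the patients, and the other half is assigned to a Cox model, which is not a ROC analysis. Followed as written, the plan runs a ROC on a sample that was not sized for it.

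Three things are left open for the main aim: which patients supply the AUC, what value it is tested against, and with what power. Because the patient set is not named, the reported AUC could be taken from either half or from the whole sample after the data have been seen.

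**Working it through.** **Inputs from the documents.** Two-sided alpha 0.05, power 80%, 60 benign and 60 malignant, AUC 0.688 (all Appendix A). Total 120 (Patients). ROC on 60 of the 120 (Statistical methods).

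**Assumptions.** 0.688 is taken as the true AUC, since Appendix A cites it without calling it the alternative. The null AUC is not stated, so 0.50 is taken first and then varied. The split of the 60 is not stated, so 30/30 is taken first and then varied.

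**Step 1: try to reproduce 80% at 60/60 with null 0.50.** The Hanley-McNeil variance for AUC A with m malignant and n benign patients is

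Var = [A(1−A) + (m−1)(Q1−A²) + (n−1)(Q2−A²)] / (mn), where Q1 = A/(2−A) and Q2 = 2A²/(1+A).

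- At A = 0.688: A² = 0.4733, Q1 = 0.5244, Q2 = 0.5608. For 60/60, Var = 0.002330 and SE = 0.04827.
- At A = 0.50: Q1 = Q2 = 0.3333. For 60/60, Var = 0.002801 and SE = 0.05292.
- Power = Φ[(0.188 − 1.960 × 0.05292) / 0.04827] = Φ(1.746) = 96.0%.

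Noether's formula, with N patients in equal groups, gives Φ[√(3N) × 0.188 − 1.960]. For N = 120 this is Φ(3.567 − 1.960) = Φ(1.607) = 94.6%.

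The stated 80% does not reproduce at null 0.50. There, 80% needs 32–38 per group, depending on the formula.

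**Step 2: the same test on 30/30.**

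- Hanley-McNeil: the SEs are 0.06857 (at 0.688) and 0.07515 (at 0.50). Power = Φ[(0.188 − 1.960 × 0.07515) / 0.06857] = Φ(0.594) = 72.4%.
- Noether: Φ(2.522 − 1.960) = Φ(0.562) = 71.3%.

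**Step 3: which null would give 80% at 60/60?** Under Hanley-McNeil it is 0.544, where the null SE is 0.05267 and (0.1439 − 1.960 × 0.05267) / 0.04827 = 0.842, that is 80%. At the same null, 30/30 has Φ[(0.1439 − 1.960 × 0.07480) / 0.06857] = Φ(−0.040) = 48.4%.

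**Step 4: range over formulas** (Noether; Hanley-McNeil and Obuchowski, each with null and alternative variances or with the alternative variance only).

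| Null AUC | Power, 60/60 | Power, 30/30 |
|---|---|---|
| 0.50 | 94.6–97.3% | 71.3–78.3% |
| 0.52 | 89.0–93.6% | 61.6–68.8% |
| 0.55 | 74.5–81.6% | 45.1–52.1% |
| 0.540–0.553 (solved to give 80% at 60/60) | 80% | 48–51% |

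At null 0.50, no split of 60 reaches 80% under these formulas. The maximum is 79.0%, at 34 malignant and 26 benign.

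**Step 5: sensitivity to spread.** The formulas fix the shape of the strain-ratio distributions, and the documents give no spread. Binormal simulation (10,000 runs, null 0.50, DeLong test), with the malignant SD equal to, 3 times or 1/3 of the benign SD, gave 92.8–96.5% at 60/60 and 67.9–75.2% at 30/30. Splits of 15/45 or 45/15 gave from about 46% to 79.5%, so imbalance can lower or raise power.

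**Step 6: precision.** The 95% CI half-width for an AUC of 0.688 is 1.96 × SE.

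- 60/60: 1.96 × 0.04827 = 0.095, interval 0.59–0.78.
- 30/30: 1.96 × 0.06857 = 0.134, interval 0.55–0.82.
- Ratio: 0.1344 / 0.0946 = 1.42.

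**The case against.** The strongest reply is that the 60-patient ROC is only a cut-off step. The text assigns it sensitivity and specificity, and names neither an AUC nor a hypothesis test for it. The AUC first appears in the end-of-study sentence, tied to the main aim that Appendix A sizes, so reading it as an estimate on all 120 is natural. On that reading there is no shortfall: against a null of 0.50, 120 patients are more than enough. This stands as a possible reading, but the plan does not say it. It also means that the test behind the 80% appears nowhere in the methods, which is the same disconnection seen from the other side.

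A second reply is that the 48–51% figure rests on a null obtained by working backwards, and no passage suggests that null. The sample may simply have been rounded up or sized on other grounds. That is fair. The figure shows how much depends on the missing null and is not an estimate of the trial's power. For the same reason no arithmetic error in Appendix A can be proved. The failure to reproduce 80% at null 0.50 shows an incomplete specification, and the excess power there is conservative.

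A third reply is that halving a sample always lowers power and widens intervals, and that a derivation/validation split is a legitimate design. Both are true. The fault is that the power statement was not carried over to the sample the ROC uses.

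**Conclusion.** The concern holds. Appendix A attaches 80% power to a ROC test on 60 plus 60 patients, the only specified ROC uses 60 in total, the end-of-study AUC has no named patient set, and no null AUC is stated. These points come from the text and need no assumption.

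The size of the consequence does rest on assumptions: a true AUC of 0.688, the null and the class split. If the AUC comes from the 60-patient ROC at 30/30, the shortfall is modest against a null of 0.50 and severe against a null near 0.55, and the confidence interval is about 42% wider than all 120 patients would allow. If the AUC is meant to come from all 120, power is adequate and what remains is that the plan does not say so. The point should be settled before analysis because it concerns the main aim.

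**What to change.** - **Statistical methods, including the end-of-study sentence:** state that the AUC with its 95% CI, and the test in Appendix A, use all 120 patients. State that any derivation/validation split serves only the cut-off, and say how the 60 are chosen and with what benign/malignant split.
- **Appendix A:** state the null AUC and the formula or R function, and correct the power to match. With a null of 0.50 and 60/60 it is about 96% (94.6–97.3% by formula, somewhat lower if the two groups differ in spread).
- **If the ROC is to stay on 60 patients:** restate its power and expected CI width for that sample under the stated null and split.

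The cost is wording in Appendix A and the Statistical methods section. Recruitment is unchanged.
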